11.4.2 Secondary Analysis

Longitudinal analysis for the relationship between QOL and the intervention will be handled by repeated measures analysis of variance modeling and multiple regressions. Finally, a logistic regression model will be used to identify which variables are most closely associated with the dependent variable of patients who experience either clinically significant deficits in QOL (one regression model). The modeling processes will include the aforementioned covariates to control for spurious correlations.

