5.5 Study Calendar

	Baseline	During 2 weeks of PR	After Hospital Discharge	At 3 and 6 months after surgery*
MRC Dyspnea scale	X			X
CRQ	X			X
LASA	X			X
Patient Log		X(1)		
CRA Contact			X(2)	X(4)
Hospital records			X(3)	

* A window of +/- 2 weeks before or after each time point for completion of the self-report measures will be allowed. The nurse/CRA should call the patient prior to mailing the questionnaire booklets. The call is to let the patient know that the questionnaires are on the way.

- 1 Patients on the intervention arm will return the completed log to local site staff at the end of the final PR visit. Patients on the control arm will be asked to mail completed patient logs to local site staff. Sites will then mail all patient logs to the address provided in Section 6.3.
- 2 The CRA will call the patient within 7 days from discharge to ask the 3 questions included in Appendix III.
- 3 Hospital records MUST include inpatient information from admissions to discharge. See Section 6.3.
- 4 The CRA will call the patient to let the patient know that the questionnaires are on the way.

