6.2 Patient questionnaire booklets

All patient questionnaire booklets for A221502 are to be ordered prior to the registration of any patients. Baseline booklets will be administered in clinic at the time that the patient is randomized. Samples of all questionnaire/booklets are available in Appendices I and II, for reference and IRB submission only. **They are not to be used for patient completion.**

Post-surgery booklets (month 3 and month 6) should be mailed by institutional staff to patients 1 week before the 3 and 6 month time points. Patients will be instructed to mail the booklets back to their registering site for entry into the iMedidata RAVE.

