11.2 Sample Size, Accrual Time, and Study Duration

11.2.1 Sample Size

A total of 194 patients (97 in each group) will be accrued to this study. This sample size includes a 10% adjustment to account for attrition and will provide at least 80% power for testing each aim of the study. Based on estimates from the pilot study, this sample size will provide 80% power to detect a 25% difference in complication rates, a 3-day difference in chest tube days, 3 day difference in length of stay, and a half standard deviation difference in QOL endpoints.

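### The plan gives no step for an unreturned 3- or 6-month QOL booklet and no missing-data method; if Section 11.4.2 means classical repeated-measures ANOVA, the QOL trajectory rests on patients who returned both

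*Combined protocol and SAP*

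**What the plan says.** **Collection.** Section 6.2: "Post-surgery booklets (month 3 and month 6) should be mailed by institutional staff to patients 1 week before the 3 and 6 month time points". The patient posts the booklet back to the registering site. The only contact tied to these booklets is in note 4 of the Section 5.5 calendar: "The CRA will call the patient to let the patient know that the questionnaires are on the way". Section 5.5 allows completion up to 2 weeks either side of each time point. Neither section mentions a reminder, a second mailing, completion by telephone or a record of why a booklet is missing.

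**Analysis.** QOL is analysed in two ways.
- Section 11.4.1 applies the methods of the primary endpoint, which Section 11.3.2 gives as a t-test or Wilcoxon test plus adjusted linear models.
- Section 11.4.2 adds a longitudinal analysis: "Longitudinal analysis for the relationship between QOL and the intervention will be handled by repeated measures analysis of variance modeling and multiple regressions".

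Neither section states the estimation method, which patients enter, or how a missing booklet or a death before 6 months is treated.

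**Allowance for loss.** Section 11.2.1: "A total of 194 patients (97 in each group) will be accrued to this study", followed by "This sample size includes a 10% adjustment to account for attrition and will provide at least 80% power for testing each aim of the study". For QOL the target is "a half standard deviation difference in QOL endpoints". Attrition is not defined.

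**The concern.** After lung resection in patients with COPD, it is plausible that those recovering poorly return fewer questionnaires, although the documents give no return rates or reasons. The arms also differ in contact before surgery: up to ten supervised sessions in one, a pedometer and a pamphlet in the other. Section 10.2 asks only for baseline and off-treatment data from registered patients who never receive the study intervention, which could also remove follow-up unevenly.

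Classical repeated-measures ANOVA, with visit as a within-patient factor, needs every visit. A patient with a month-3 booklet and no month-6 booklet would contribute nothing. The trajectory result would then describe a selected group, and data already collected would be discarded. A booklet not completed in its window cannot be recovered at analysis, so the collection gap has to be closed while patients are in follow-up.

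**Working it through.** **1. The plan's own figure.** Inputs from Sections 11.2.1 and 11.3.2: 97 per arm, 10% attrition, 0.5 SD, two-sided 0.05. A two-sample t-test with 80% power for 0.5 SD needs 64 per arm, or 64 / 0.9 = 71.1, so 72 per arm with the allowance. The 97 is therefore not the half-SD sample size, but the promise of at least 80% is met: 97 × 0.9 = 87 per arm gives 90.6%.

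**2. Loss of numbers.** The documents give no return rate, so the rates below are assumptions, taken as independent between visits and starting from 97 per arm. With return rate r, the number with the booklet at a given visit is 97r, with both booklets 97r², and with at least one 97(1 − (1 − r)²). Power is approximately Φ(0.5√(n/2) − 1.96). For n = 70 this is Φ(2.958 − 1.960) = 84.1%, and the exact t value is 83.6%. The table uses exact t values for a comparison at one time point.

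| Non-return per booklet | Both booklets | Power | Booklet at the visit tested | Power | At least one |
|---|---|---|---|---|---|
| 10% | 79 | 88% | 87 | 91% | 96 |
| 15% | 70 | 84% | 82 | 89% | 95 |
| 20% | 62 | 79% | 78 | 87% | 93 |

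Requiring both booklets costs 3 to 8 points of power and leaves out 17 to 31 patients per arm who returned one (96 − 79 = 17; 93 − 62 = 31). Power stays close to 80% even in the last row.

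**3. Selective return.** A large-sample simulation (400,000 per arm) assumed a true effect of 0.5 SD at both visits, correlation 0.6 between time points, and return that falls as QOL falls. Return at 6 months was about 76 to 85%, and 60 to 72% returned both. Return depended either on QOL already observed or on current QOL.

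| Link between health and return | Effect on change at 6 months, both booklets | 6-month contrast, both booklets | 6-month contrast, all 6-month booklets |
|---|---|---|---|
| None | 0.50 | 0.50 | 0.50 |
| Same in both arms | 0.48 to 0.50 | 0.42 to 0.48 | 0.44 to 0.49 |
| Stronger in the control arm | 0.42 to 0.56 | 0.20 to 0.35 | 0.30 to 0.41 |

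In the last row the effect on change was too large (0.54 to 0.56) when return depended on earlier observed QOL, and too small (0.42 to 0.44) when it depended on current QOL. The 6-month contrast shrank because the healthier control patients were over-represented; with the stronger link in the intervention arm it would be expected to move the other way. Using all 6-month booklets reduced the distortion of that contrast but did not remove it. The mixed model itself was not simulated.

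**The case against.** Four objections have force.

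- **The plan does not say patients are dropped.** Repeated-measures ANOVA modelling can also mean a likelihood-based model that keeps one-visit patients. A reader might infer a stated complete-case rule; there is none. What stands is that the two readings use different analysis sets and the plan does not choose.
- **Not every QOL result needs both booklets.** The Section 11.4.1 tests need only the booklet at the visit tested. The restriction to patients with both applies to the longitudinal analysis under its classical reading. The single-visit tests are still limited to those who responded.
- **Silence is not a rule against reminders.** Section 6.1 mentions a Schedule of Forms and Section 10.2 a Data Submission Schedule, neither of which is in the documents. Sites may chase late forms, but the protocol text does not ask them to.
- **Power is largely protected.** A reader might infer a clear breach of the 80% promise by taking non-return off 87 per arm: 87 × 0.9², 0.85² and 0.8² leave 70, 63 and 56, with power of 84%, 80% and 75%. That may count loss twice, since unreturned booklets may be what the 10% covers. These are also single-visit figures. If the arm effect is averaged over both visits, its variance is multiplied by (1 + ρ)/2; with an assumed ρ of 0.5 to 0.7, power is 86 to 90% at 63 per arm and 81 to 86% at 56.

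**Conclusion.** The point holds in limited form. The protocol describes no action on an unreturned 3- or 6-month booklet, although about three weeks separate mailing from the end of the window. The SAP text gives no method for missing QOL data or for deaths. If Section 11.4.2 means classical repeated-measures ANOVA, the result for objective 2.2.2 comes only from patients with both booklets.

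The size of any bias cannot be derived from the documents. Under the simulation's assumptions it is small when health affects return equally in both arms. It can be large when the arms differ: a 6-month contrast of 0.20 to 0.35 against a true 0.50. A reader might infer that the bias favours the arm losing more unwell patients; the documents do not fix the direction, and the simulated effect on change moved both ways. The loss of power is modest and secondary. The consequence is confined to a secondary objective, but the remedy is cheap and its collection part cannot be applied afterwards.

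**What to change.** **Sections 5.5 and 6.2.** If a booklet is not back one week after its time point, the CRA makes one reminder call within the existing window. This applies in both arms, whether or not the patient completed the rehabilitation. If the booklet is still missing, the reason is recorded. Reconcile the reduced data submission in Section 10.2 with follow-up by assigned arm.

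**Section 11.4.2.** Replace repeated-measures ANOVA with a likelihood-based mixed model for repeated measures, with baseline score, arm, visit, arm-by-visit and the stratification factors. Analyse by assigned arm, using every patient with at least one post-surgery booklet. Report return rates by arm and visit, state how deaths before 6 months are handled, and add one missing-not-at-random sensitivity analysis. Say whether the Section 11.4.1 or the Section 11.4.2 analysis is the main QOL analysis.

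**Cost.** SAP wording, and one call per late booklet by staff who already phone these patients. With 194 × 2 = 388 booklets and an assumed 10 to 20% late, that is about 39 to 78 calls over the whole trial. The mixed model still assumes data are missing at random, so it reduces but does not remove bias from selective return; that is why the reminder and the sensitivity analysis are needed as well.

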9.0 MEASURES

9.1 Chronic Respiratory Questionnaire (CRQ):

A 20-question inventory assessing the areas of dyspnea, fatigue, emotion, and feelings of mastery. The fatigue, emotion, and mastery subscales ask the patient to rate how often in the last two weeks they have been afflicted with a particular feeling or experience on a scale of 1 to 7, with higher ratings indicating less symptom impairment. The dyspnea subscale gives an additional option of indicating that a particular activity has not been done.²⁴⁻²⁷ The CRQ takes approximately 10 minutes to complete.

9.2 MRC: Medical Research Council Dyspnea Score (MRC):

A 5 statement questionnaire where the patient selects the answer that most closely describes the level of physical activity that precipitates their shortness of breath. The highest selected statement (more severe) is the score. The MRC Dyspnea Scale takes less than 5 minutes to complete.

9.3 Linear Analog Self-Assessment (LASA):

A 5 question inventory measuring well-being on a scale of 1 (as bad as it can be) to 10 (as good as it can be). The LASA takes less than 5 minutes to complete.

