11.3.2 Analysis Plan

Differences in length of stay between arms will be tested using a two-sample, two-sided t-test. Wilcoxon nonparametric testing will be used for analyzing continuous outcomes that are skewed and not approximately normally distributed. Fisher's exact tests will be used to test for differences in categorical variables between arms. All tests will be two-sided with a 0.05 significance level. Linear models will be created to test the effects of treatment after adjusting for the baseline characteristics of age, gender, and lung function.

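### The model that identifies variables associated with poor QOL uses an undefined yes/no deficit instead of the full score, which costs this supplementary analysis power

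*Combined protocol and SAP*

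**What the plan says.** Section 11.4.2 closes its list of analyses with a predictor model: "a logistic regression model will be used to identify which variables are most closely associated with the dependent variable". The dependent variable is described as "patients who experience either clinically significant deficits in QOL (one regression model". The word 'either' has no second alternative, and the section does not say which score, which visit or which cut makes a deficit.

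The same section first plans repeated measures ANOVA and multiple regressions, directed at how QOL relates to the intervention. It ends by saying that the modelling will include the covariates already named; Section 11.3.2 names age, gender and lung function. Section 11.4.1 analyses the QOL outcomes in the same way as the primary endpoint, which under 11.3.2 means a t-test or Wilcoxon test plus adjusted linear models.

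The fuller outcome is already collected. Section 9.1 describes CRQ responses "on a scale of 1 to 7, with higher ratings indicating less symptom impairment", and the calendar in 5.5 schedules the CRQ at baseline, 3 and 6 months. Section 11.2.1 sizes QOL as a continuous outcome: "a half standard deviation difference in QOL endpoints".

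**The concern.** The stated purpose of the logistic model is to find the variables most closely associated with a poor QOL outcome. Reducing a multi-item score to yes/no treats a patient just below the cut like one far below it, and a patient just above like one far above. Real associations are then missed more often, and any ranking of variables is noisier, although the full score is in the database at no extra cost.

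Because the deficit is undefined, the result also depends on a cut that could be chosen after the data are seen. Section 11.4.1 gives 0.5 CRQ points as the minimal clinically important difference, but presents it as a difference to detect and not as the threshold at which an individual patient has a deficit.

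What is at stake is the quality of one supplementary analysis, not a trial objective.

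**Working it through.** **Inputs from the documents.** Two-sided 0.05 (11.3.2: "All tests will be two-sided with a 0.05 significance level"). Sample size (11.2.1): "A total of 194 patients (97 in each group) will be accrued to this study". Attrition (11.2.1): "This sample size includes a 10% adjustment to account for attrition". So 97 × 0.9 = 87.3, about 87 per arm and 174 in all.

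**Assumptions.** The deficit share is not in the documents; 20% to 50% is taken as the main range, with 10% and 5% also shown. The score is taken as roughly normal. The 80% starting point for a predictor is a benchmark only.

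**Step 1: the plan's own figure.** For a half-SD arm difference, n per arm = 2 × (1.960 + 0.842)² / 0.5² = 62.8, so 63. With 10% attrition this is 63 / 0.9 = 70 per arm, or 140 in all. At 87 per arm, power = Φ(0.5 × √(87/2) − 1.960) = Φ(3.298 − 1.960) = 91%. That is not 80%, but it is consistent with the plan's 'at least 80%'. It concerns the comparison of arms on the full score. No power is stated for finding predictors.

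**Step 2: information kept after the cut.** For a normal score cut so that a share p falls below it, the efficiency relative to the full score is E = φ(z_p)² / [p(1 − p)]. A predictor with 80% power on the full score has noncentrality 1.960 + 0.842 = 2.802. After the cut, power = Φ(2.802 × √E − 1.960). The sample size needed for equal power is multiplied by 1/E.

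| Deficit share | φ(z_p) | E | 2.802 × √E | Power | 1/E |
|---|---|---|---|---|---|
| 50% | 0.399 | 0.637 | 2.235 | 60.8% | 1.57 |
| 30% | 0.348 | 0.576 | 2.126 | 56.6% | 1.74 |
| 20% | 0.280 | 0.490 | 1.961 | 50.0% | 2.04 |
| 10% | 0.176 | 0.342 | 1.639 | 37.4% | 2.92 |
| 5% | 0.103 | 0.224 | 1.326 | 26.3% | 4.47 |

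**Step 3: simulation check.** With 174 patients, 2,500 runs per setting and three further covariates in each model, the linear model had 78% to 80% power. The logistic model had 59% to 62% at a 50% share, 55% to 57% at 30%, 46% to 50% at 20% and 32% to 38% at 10%. The formula holds up.

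**Step 4: dependence on the benchmark.** Let a continuous predictor have correlation r with QOL, with noncentrality atanh(r) × √(174 − 3). Then r = 0.21 gives about 80% on the full score. At r = 0.15 the full score gives about 51% and the cut 28% to 35% (shares 20% to 50%). At r = 0.30 the figures are 98% and 81% to 90%. A strong predictor would usually be found either way; the loss matters most for moderate ones.

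**The case against.** Four points can be made for the plan.

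*No objective depends on this model.* Objective 2.2.2 is the effect of the intervention on QOL, and that is tested on the full score. The claim "will provide at least 80% power for testing each aim of the study" is about the aims, and predictor identification is not among them. This stands, and it limits the point to a supplementary analysis.

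*The covariates also enter the continuous models.* A reader might infer that everything the trial learns about predictors of QOL rests on the dichotomised model alone. The documents do not support that: age, gender and lung function are also in the adjusted linear models, and the closing sentence of 11.4.2 applies to the modelling generally. What remains is narrower. In those models the variables serve as adjustment, and the logistic model is the only one given the task of identifying associated variables.

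*The deficit is a question in its own right.* Which patients end with a clinically important deficit is legitimate to ask, and a model of the mean score does not give the odds of one directly. This stands, and it is why the logistic model should be kept.

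*The power figures rest on assumptions.* A reader might take a fall from 80% to 50-61% as a property of the plan. It is not, because both the starting power and the deficit share are assumed. What does not depend on the starting power is the information kept, at most 64% under a normal score whatever the cut.

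A reader might also infer that the treatment comparison on QOL is weakened. At a half SD with 87 per arm, the arm term in the logistic model would have 64%, 71% and 75% power at overall deficit shares of 20%, 30% and 50%, against 91% on the full score. But the plan judges the intervention on the full score, so that loss falls on a test it does not rely on.

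**Conclusion.** The point holds as a minor one. The model charged with identifying associated variables uses a yes/no outcome that is both undefined and less informative than the score already collected. Under a roughly normal score and deficit shares of 20% to 50%, it keeps 49% to 64% of the information, equivalent to needing about 1.6 to 2.0 times the patients. Rarer deficits make this worse. The size in any real case depends on the deficit share, the shape of the score and the strength of the predictor, none of which the documents give. The length-of-stay analysis and the QOL arm comparisons are not touched, and nothing here suggests that 194 patients is the wrong number.

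**What to change.** In Section 11.4.2:

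- State that the conclusion about associated variables is drawn from a linear or mixed model of the continuous 3- and 6-month CRQ domain scores, with arm, the baseline score, age, gender and lung function.
- Keep the logistic deficit model as a supportive analysis. Fix its instrument, time point and cut before the data are examined, and complete or remove the dangling 'either'.
- Report the proportion with a deficit by arm, with a 95% confidence interval.

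The cost is SAP wording only, with no new data or patients. The one small downside is that the lead coefficients are in CRQ points instead of odds of a deficit; the supportive model and the proportions keep the clinical reading.

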11.5 Study Monitoring

11.5.1 Adverse Event Stopping Rule

Not applicable.

11.5.2 Accrual Monitoring Stopping Rule

Slow Accrual: Patient accrual will be closely monitored by the investigators and secondary statistician on a monthly basis. If the accrual rate falls below 50% of expected accrual rate, investigators will carefully review feedback from sites and consider taking measures to encourage patient enrollment.

11.5.3 This study will be monitored by the Alliance Data Safety Monitoring Board (DSMB), an NCI-approved functioning body. Reports containing efficacy, adverse event, and administrative information will be provided to the DSMB every month as per NCI guidelines.

11.6 Study Reporting

At study activation, this study will have been registered within the “ClinicalTrials.gov” web site. The Primary and Secondary Endpoints (i.e., “Outcome Measures”) along with other required information for this study will be reported on ClinicalTrials.gov.

11.7 Descriptive Factors

None.

11.8 Inclusion of Women and Minorities

Inclusion of Women: Based upon the gender distribution of patients from past studies and the gender distribution with ICD-9 codes for COPD/ lung cancer, we anticipate a female to male ratio of 5/6 ratio.

DOMESTIC PLANNED ENROLLMENT REPORT						
Racial Categories	Ethnic Categories				Total	
	Not Hispanic or Latino		Hispanic or Latino			
	Female	Male	Female	Male		
American Indian/ Alaska Native	1	1	0	0	2	
Asian	5	3	1	1	10	
Native Hawaiian or Other Pacific Islander	1	1	0	0	2	
Black or African American	14	9	1	1	25	
White	80	57	4	4	145	
More Than One Race	4	3	2	1	10	
Total	105	74	8	7	194	

APPENDIX I

LINEAR ANALOGUE SELF ASSESSMENT

Directions: Please circle the number (0-10) best reflecting your response to the following that describes your feelings **during the past week, including today**.

How would you describe:

1. Your overall Quality of Life?

As bad as it can be										As good as it can be
0	1	2	3	4	5	6	7	8	9	10

2. Your overall mental (intellectual) well being?

As bad as it can be										As good as it can be
0	1	2	3	4	5	6	7	8	9	10

3. Your overall physical well being?

As bad as it can be										As good as it can be
0	1	2	3	4	5	6	7	8	9	10

4. Your overall emotional well being?

As bad as it can be										As good as it can be
0	1	2	3	4	5	6	7	8	9	10

5. Your level of social activity?

As bad as it can be										As good as it can be
0	1	2	3	4	5	6	7	8	9	10

6. Your overall spiritual well being?

As bad as it can be										As good as it can be
0	1	2	3	4	5	6	7	8	9	10

Medical Research Council (MRC) Breathlessness Scale

INSTRUCTIONS: Please read each statement carefully. If you agree with the statement please circle **YES**. If you disagree with the statement please circle **NO**. Please be sure to answer all the questions. Only circle 1 answer for each question. If you make a mistake, place an **X** over the incorrect answer and be sure to circle the correct answer.

		Description
YES	NO	Are you ever troubled by breathlessness except on strenuous exertion?
YES	NO	(If yes) Are you short of breath when hurrying on the level or walking up a slight hill?
YES	NO	(If yes) do you have to walk slower than most people on the level? Do you have to stop after a mile or so (or after $\frac{1}{4}$ hour) on the level at your own pace?
YES	NO	(If yes) Do you have to stop for breath after walking about 100 yds. (or after a few minutes) on the level?
YES	NO	(If yes) Are you too breathless to leave the house, or breathless after undressing?

<http://www.mrc.ac.uk/research/facilities/mrc-scales/mrc-dyspnoea-scale-mrc-breathlessness-scale/>

Chronic Respiratory Questionnaire (CRQ-SAS)

First Administration

**McMaster University
Canada**

Chronic Respiratory Questionnaire

**Self-Administered Standardized Format
(CRQ-SAS)**

First Administration

Version 07July15 Copyright © 2001 McMaster University, Hamilton, Ontario, Canada. The Chronic Respiratory Questionnaire Self-Administered Standardized (CRQ-SAS) and Self-Administered Individualized (CRQ-SAI), Principal authors Drs. G.H. Guyatt, and Dr. H.J. Schünemann, are the copyright of McMaster University (Copyright ©2001, McMaster University). The CRQ has been provided under license from McMaster University and must not be copied, distributed or used in any way without the prior written consent of McMaster University. Contact the McMaster Industry Liaison Office at McMaster University, email: [contact] for licensing details.

**CHRONIC RESPIRATORY QUESTIONNAIRE - SELF ADMINISTERED - STANDARDIZED
ACTIVITIES - "CRQ-SAS"**

Participant ID:

Date

	
----------------------	----------------------

	
----------------------	----------------------

			
----------------------	----------------------	----------------------	----------------------

DAY

MONTH

YEAR

CHRONIC RESPIRATORY QUESTIONNAIRE -SAS- FIRST ADMINISTRATION 1(10)

This questionnaire is designed to find out how you have been feeling during the last 2 weeks. In the first section, you will be asked to answer questions about activities which make some people feel short of breath. In the next section, you will answer questions about your mood and how you have been feeling.

Please read these instructions for completing this questionnaire:

- Please read each question carefully and then place an "x" in the box beside the answer that best describes you.
- If you are unsure about how to answer a question, please give the best answer you can.
- If you would like to change an answer, put a line through the box you want to change. Place an "x" in the box beside the option you would like to choose instead.
- There are no right or wrong answers.
- Your answers to this questionnaire will be kept confidential.

Please continue on the next page.

Version 07July15 Copyright © 2001 McMaster University, Hamilton, Ontario, Canada. The Chronic Respiratory Questionnaire Self-Administered Standardized (CRQ-SAS) and Self-Administered Individualized (CRQ-SAI), Principal authors Drs. G.H. Guyatt, and Dr. H.J. Schünemann, are the copyright of McMaster University (Copyright ©2001, McMaster University). The CRQ has been provided under license from McMaster University and must not be copied, distributed or used in any way without the prior written consent of McMaster University. Contact the McMaster Industry Liaison Office at McMaster University, email: [contact] for licensing details.

1 of 10

**CHRONIC RESPIRATORY QUESTIONNAIRE - SELF ADMINISTERED - STANDARDIZED
ACTIVITIES - "CRQ-SAS"**

Date

--	--

--	--

--	--	--	--

 DAY MONTH YEAR

CRQ-SAS- 1ST ADMINISTRATION

Below is a list of activities which make some people with lung problems feel short of breath.

For each of the activities below, place an "x" in the box that best describes how much shortness of breath you have had while doing that activity during the **LAST 2 WEEKS**.

The last column has been provided for you to indicate if you have **NOT DONE** an activity during the last two weeks.

(Place an "x" in one box on each line)

ACTIVITIES:	Extremely short of breath	Very short of breath	Quite a bit short of breath	Moderate shortness of breath	Some shortness of breath	A little shortness of breath	Not at all short of breath	Not Done
1 Feeling emotional such as angry or upset	 1	 2	 3	 4	 5	 6	 7	 8
2 Taking care of your basic needs (bathing, showering, eating or dressing)	 1	 2	 3	 4	 5	 6	 7	 8
3 Walking	 1	 2	 3	 4	 5	 6	 7	 8
4 Performing chores (such as housework, shopping groceries)	 1	 2	 3	 4	 5	 6	 7	 8
5 Participating in social activities	 1	 2	 3	 4	 5	 6	 7	 8

Please continue to the next page.

Version 07July15 Copyright © 2001 McMaster University, Hamilton, Ontario, Canada. The Chronic Respiratory Questionnaire Self-Administered Standardized (CRQ-SAS) and Self-Administered Individualized (CRQ-SAI), Principal authors Drs. G.H. Guyatt, and Dr. H.J. Schünemann, are the copyright of McMaster University (Copyright ©2001, McMaster University). The CRQ has been provided under license from McMaster University and must not be copied, distributed or used in any way without the prior written consent of McMaster University. Contact the McMaster Industry Liaison Office at McMaster University, email: [contact] for licensing details.

2 of 10

These next questions ask you about your energy in general and how your mood has been during the **LAST 2 WEEKS**. Please put an "x" in a box, from 1 to 7, that best describes how you have felt.

6. In general, how much of the time during the **LAST 2 WEEKS** have you felt frustrated or impatient?

1. All of the time		
2. Most of the time		
3. A good bit of the time		
4. Some of the time		(Place an "x" in one box only)
5. A little of the time		
6. Hardly any of the time		
7. None of the time		

7. How often during the **LAST 2 WEEKS** did you have a feeling of fear or panic when you had difficulty getting your breath?

1. All of the time		
2. Most of the time		
3. A good bit of the time		
4. Some of the time		(Place an "x" in one box only)
5. A little of the time		
6. Hardly any of the time		
7. None of the time		

Please continue to the next page

8. What about fatigue? How tired have you felt over the **LAST 2 WEEKS**?

1. Extremely tired	
2. Very tired	
3. Quite a bit of tiredness	
4. Moderately tired	
5. Somewhat tired	
6. A little tired	
7. Not at all tired	

(Place an "x" in one box only)

9. How often during the **LAST 2 WEEKS** have you felt embarrassed by your coughing or heavy breathing?

1. All of the time	
2. Most of the time	
3. A good bit of the time	
4. Some of the time	
5. A little of the time	
6. Hardly any of the time	
7. None of the time	

(Place an "x" in one box only)

Please continue to the next page

10. In the **LAST 2 WEEKS**, how much of the time did you feel very confident and sure that you could deal with your illness?

1. None of the time
2. A little of the time
3. Some of the time
4. A good bit of the time (Place an "x" in one box only)
5. Most of the time
6. Almost all of the time
7. All of the time

11. How much energy have you had in the **LAST 2 WEEKS**?

1. No energy at all
2. A little energy
3. Some energy
4. Moderately energetic (Place an "x" in one box only)
5. Quite a bit of energy
6. Very energetic
7. Full of energy

Please continue to the next page

12. In general, how much of the time did you feel upset, worried, or depressed during the **LAST 2 WEEKS?**

1. All of the time	
2. Most of the time	
3. A good bit of the time	
4. Some of the time	
5. A little of the time	
6. Hardly any of the time	
7. None of the time	

(Place an "x" in one box only)

13. How often during the **LAST 2 WEEKS** did you feel you had complete control of your breathing problems?

1. None of the time	
2. A little of the time	
3. Some of the time	
4. A good bit of the time	
5. Most of the time	
6. Almost all of the time	
7. All of the time	

(Place an "x" in one box only)

Please continue to the next page

14. How much of the time during the **LAST 2 WEEKS** did you feel relaxed and free of tension?

1. None of the time
2. A little of the time
3. Some of the time
4. A good bit of the time (Place an "x" in one box only)
5. Most of the time
6. Almost all of the time
7. All of the time

15. How often during the **LAST 2 WEEKS** have you felt low in energy?

1. All of the time
2. Most of the time
3. A good bit of the time
4. Some of the time (Place an "x" in one box only)
5. A little of the time
6. Hardly any of the time
7. None of the time

Please continue to the next page

16. In general, how often during the **LAST 2 WEEKS** have you felt discouraged or down in the dumps?

1. All of the time
2. Most of the time
3. A good bit of the time
4. Some of the time
5. A little of the time
6. Hardly any of the time
7. None of the time

(Place an "x" in one box only)

17. How often during the **LAST 2 WEEKS** have you felt worn out or sluggish?

1. All of the time
2. Most of the time
3. A good bit of the time
4. Some of the time
5. A little of the time
6. Hardly any of the time
7. None of the time

(Place an "x" in one box only)

Please continue to the next page

18. How happy, satisfied, or pleased have you been with your personal life during the **LAST 2 WEEKS?**

1. Very dissatisfied, unhappy most of the time
2. Generally dissatisfied, unhappy
3. Somewhat dissatisfied, unhappy
4. Generally satisfied, pleased (Place an "x" in one box only)
5. Happy most of the time
6. Very happy most of the time
7. Extremely happy, could not be more satisfied or pleased

19. How often during the **LAST 2 WEEKS** did you feel upset or scared when you had difficulty getting your breath?

1. All of the time
2. Most of the time
3. A good bit of the time
4. Some of the time (Place an "x" in one box only)
5. A little of the time
6. Hardly any of the time
7. None of the time

Please continue to the next page

20. In general, how often during the **LAST 2 WEEKS** have you felt restless, tense, or uptight?

1. All of the time
2. Most of the time
3. A good bit of the time
4. Some of the time
5. A little of the time
6. Hardly any of the time
7. None of the time

(Place an "x" in one box only)

THANK YOU

Version 07July15 Copyright © 2001 McMaster University, Hamilton, Ontario, Canada. The Chronic Respiratory Questionnaire Self-Administered Standardized (CRQ-SAS) and Self-Administered Individualized (CRQ-SAI), Principal authors Drs. G.H. Guyatt, and Dr. H.J. Schünemann, are the copyright of McMaster University (Copyright ©2001, McMaster University). The CRQ has been provided under license from McMaster University and must not be copied, distributed or used in any way without the prior written consent of McMaster University. Contact the McMaster Industry Liaison Office at McMaster University, email: [contact] for licensing details

10 of 10

